8.2.4 Tanner staging

Tanner staging ([Appendix H](#)) will also be assessed at Cycle 1 Day 1 and subsequently at visits where radiological efficacy assessments are made (see Section 8.1).

8.2.5 Electrocardiograms

Single resting 12-lead electrocardiograms (ECGs) will be recorded at screening and as clinically indicated throughout the study (see the SoAs). ECGs should be obtained after the patient has been in a supine position for 5 minutes and recorded while the patient remains in that position.

In case of clinically significant ECG abnormalities, including a QTcF value >470 ms calculated using Fridericia's formula, an additional 12-lead ECG should be obtained over a brief period (eg, 30 minutes) to confirm the finding.

Situations in which ECG results should be reported as AEs are described in Section 8.3.7.

8.2.6 Early patient review for safety

Patients should be attending scheduled visits on Cycle 1 Day 15 and Cycle 2 Day 15. It is also recommended patients are contacted on Cycle 3 Day 15 to ensure early identification and management of toxicities.

8.2.7 Performance status

Karnofsky performance status (Appendix I) will be assessed in patients ≥ 16 years of age and Lansky play performance scale (Appendix J) will be assessed in patients ≥ 1 and < 16 years of age at the times specified in the assessment schedules in line with the SoA.

Any significant change from baseline or screening must be reported as an AE.

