3. OBJECTIVES AND ENDPOINTS

Table 5 Study objectives

Primary Objective (Dose-finding phase):	Endpoint/Variable:
To determine the adult equivalent exposure/MTD/recommended Phase II pediatric dose of durvalumab in combination with tremelimumab and durvalumab as monotherapy following combination therapy.	Based on PK parameters (including C_{max} , C_{min} , AUC, and others), identify the adult equivalent exposure/MTD of durvalumab in combination with tremelimumab and durvalumab as monotherapy following combination therapy, among children and young adults from birth to <18 years of age with advanced solid tumors, using a q4w dosing schedule. Time of RP2D assessment will be at the end of the dose-finding phase, when sufficient numbers of evaluable samples have been accrued.
To determine the safety profile of durvalumab in combination with tremelimumab and durvalumab as monotherapy following combination therapy.	Identify the safety and tolerability of durvalumab in combination with tremelimumab and durvalumab as monotherapy following combination therapy at the adult equivalent exposure/MTD among children and young adults from birth to <18 years of age with advanced solid tumors, using a q4w dosing schedule. Endpoints include AEs, vital signs, physical examinations, ECGs, and laboratory evaluations.
Primary Objective (Dose-expansion phase):	Endpoint/Variable:
To determine the preliminary antitumor activity of durvalumab in combination with tremelimumab and durvalumab as monotherapy following combination therapy, at the recommended dose, using cohort-specific response criteria (eg, RECIST 1.1).	Objective response rate as determined by the Investigator assessed RECIST 1.1 or alternative pre-specified tumor-specific response rates for different scoring systems.

	
Assessment of antitumor activity will be specific to tumor cohort, eg, Investigator assessed RECIST 1.1.
 
Additional efficacy endpoints that will be collected include DoR, BoR, DCR, PFS, APF12, and APF18 based on RECIST 1.1 assessed by the Investigator, and OS, OS12, and OS24 as appropriate to each individual cohort.

Secondary Objective (Dose-finding and Dose-expansion phases):	Endpoint/Variable:

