8.3.7 Adverse events based on examinations and tests

The results from the Clinical Study Protocol mandated laboratory tests and vital signs will be summarized in the clinical study report (CSR). Deterioration as compared to baseline in protocol mandated laboratory values, vital signs, physical examination findings, or ECG should therefore only be reported as AEs if they fulfill any of the SAE criteria or are the reason for discontinuation of treatment with the IP.

If deterioration in a laboratory value/vital sign is associated with clinical signs and symptoms, the sign or symptom will be reported as an AE and the associated laboratory result/vital sign will be considered as additional information. Wherever possible, the reporting Investigator uses the clinical, rather than the laboratory term (eg, anemia versus low hemoglobin value). In the

absence of clinical signs or symptoms, clinically relevant deteriorations in non-mandated parameters should be reported as AE(s).

Deterioration of a laboratory value, which is unequivocally due to PD, should not be reported as an AE/SAE.

Any new or aggravated clinically relevant abnormal medical finding at a physical examination as compared with the baseline assessment will be reported as an AE unless unequivocally related to the disease under study, see Sections 8.3.9 and 8.3.10.

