8.3.9 Disease under study

Events which are unequivocally due to disease under study should not be reported as an AE during the study unless they meet SAE criteria or lead to discontinuation of the IP.

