8.3.10 Disease progression

Disease progression can be considered as a worsening of a patient's condition attributable to the disease for which the IP is being studied. It may be an increase in the severity of the disease under study and/or increases in the symptoms of the disease. The development of new, or progression of existing metastasis to the primary cancer under study should be considered as PD and not an AE. Events, which are unequivocally due to PD, should not be reported as an AE during the study.

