4.2.3.8 Other safety data

Other safety data will be listed and/or summarized:

- Tanner stage
- Performance status (Karnofsky or Lansky – the scale appropriate to the patient at the time of screening will be used through the study)

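### Protocol 8.2.7 makes any significant performance-status change an AE, while 8.3.9 and 8.3.10 exclude events unequivocally due to disease or progression; nothing supplied says which rule prevails

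*Protocol*

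**What the plan says.** Protocol 8.2.7 schedules Karnofsky scores for patients aged 16 or over and Lansky scores for those aged 1 to under 16, and then adds: "Any significant change from baseline or screening must be reported as an AE".

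Protocol 8.3.9 rules: "Events which are unequivocally due to disease under study should not be reported as an AE during the study unless they meet SAE criteria", with a further exception for events that lead to discontinuation of study drug. Protocol 8.3.10 states: "Events, which are unequivocally due to PD, should not be reported as an AE during the study". On what progression can look like, it says: "It may be an increase in the severity of the disease under study and/or increases in the symptoms of the disease".

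The other safety assessments are handled differently. Protocol 8.2.1 (examinations), 8.2.2 (laboratory), 8.2.3 (vital signs) and 8.2.5 (ECG) each send the reader to 8.3.7; the ECG section reads: "Situations in which ECG results should be reported as AEs are described in Section 8.3.7". In 8.3.7, a new or aggravated examination finding "will be reported as an AE unless unequivocally related to the disease under study, see Sections 8.3.9 and 8.3.10", and a laboratory deterioration unequivocally due to progression is also excluded. Section 8.3.7 does not mention performance status.

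For the dose-finding safety objective, Protocol Section 3 states: "Endpoints include AEs, vital signs, physical examinations, ECGs, and laboratory evaluations". AEs are also an endpoint of the dose-expansion safety objective. SAP 4.2.3.2 tabulates patients by preferred term and gives total AE counts. SAP 4.2.3.8 separately lists and/or summarises "Performance status (Karnofsky or Lansky" scores.

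**The concern.** A site that follows 8.2.7 to the letter records a progression-driven fall in performance status as an AE. A site that follows 8.3.10 to the letter does not. Both comply with the protocol. With about 20 centres (Protocol 4.1), the AE tables could then mix toxicity with disease progression in proportions that depend on which section each site read.

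Two further gaps in 8.2.7 widen the room for variation. *Significant* is undefined. The reference is baseline or screening, although both Screening and Cycle 1 Day 1 carry a scheduled score (Tables 1 and 2) and the two can differ.

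What is at stake is the content of an endpoint in the safety objectives of both phases, in cohorts small enough that one patient is visible in a percentage.

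**Working it through.** There is no planned figure to reproduce. The check is a comparison of the rules, followed by simple arithmetic on size.

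**1. One case under each rule.** Take a significant, non-serious decline, unequivocally due to progression, that does not lead to discontinuation.

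| Rule | Is it an AE? |
|---|---|
| 8.2.7 | Yes, mandatory |
| 8.3.9 (disease under study) | No; neither exception applies |
| 8.3.10 (progression) | No |
| 8.3.7 (examinations and tests) | Does not name performance status |

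The rules give opposite answers, and no supplied section ranks them.

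**2. Where they do not conflict.** A decline that is not unequivocally due to disease is outside both exclusions. A decline due to the disease that meets SAE criteria or leads to discontinuation stays reportable under 8.3.9. A drug-related decline is reportable on any reading. The conflict is confined to the case in step 1.

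**3. Can the case arise inside the AE window?** Yes. Performance status is scored at every on-treatment visit, at End of Treatment and at Day 30 after the last dose (Tables 1 to 3). Treatment continues between first progression and its confirmation (Protocol 8.1), and combination retreatment after progression is allowed (Protocol 6.1.4). SAP 3.3.1 counts AEs up to 90 days after the last dose, with one set of tables stopping at subsequent therapy.

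**4. Which outputs move.** Preferred-term rates and AE counts (SAP 4.2.3.2) move. DLTs should not: Protocol 4.1.2 requires attribution to study drug and no alternate etiology, so a disease-caused decline fails under either reading.

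**5. Size per patient.** Inputs are the planned evaluable numbers in Protocol 9.2: SARCOMA 26 in full and 11 in stage 1; STO 10. The shift in a preferred-term rate is k/n for k patients recorded differently.

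- SARCOMA, full: 1/26 = 3.8 points
- SARCOMA, stage 1: 1/11 = 9.1 points
- STO: 1/10 = 10 points

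If 1 to 5 patients were affected (an assumption), the range is 1/26 to 5/26 = 3.8 to 19.2 points in SARCOMA, and 1/10 to 5/10 = 10 to 50 points in STO.

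The real denominator is the safety analysis set, which also holds non-evaluable patients. Protocol 9.2 expects up to 43 dosed for 36 evaluable, a ratio of 43/36 = 1.19. On that ratio 26 becomes about 31 (1/31 = 3.2 points) and 10 becomes about 12 (1/12 = 8.3 points). The order of magnitude is unchanged.

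**The case against.** The strongest reply is that the sections can be read together. Section 8.3 governs AE collection, makes the investigator responsible for staff knowing it, and has sites record events that meet the AE definition in Appendix B. Section 8.3.6 is also worded without exceptions and is naturally read subject to 8.3.9 and 8.3.10; 8.2.7 could be read the same way. This is reasonable, but 8.2.7 does not say it, and the parallel assessments have an explicit link that 8.2.7 lacks. Appendix B was not in the supplied text, so a reconciling statement there cannot be excluded.

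It is also fair that outputs aimed at toxicity are largely protected. SAP 4.2.3.2 tabulates causally related AEs separately, although SAP 3.3.1 treats a missing causality as related. For analysis, baseline is already the last pre-dose value (Protocol 9.5.1, SAP 4.1.2); what remains is the instruction to sites.

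A reader might infer more than the documents support:

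- *That a large share of patients is affected.* The paediatric pembrolizumab study described in Protocol 2.2.1 had 12-month PFS of 10.2%. But PFS also counts radiological progression without functional decline, the drug and population differ, and performance status is scheduled only to Day 30 after the last dose. No passage gives the frequency or causes of performance-status decline.
- *That 8.2.7 adds only misclassified events.* It also captures drug-related decline, which belongs in the AE tables.
- *That improvements will be recorded as AEs.* The wording gives no direction, but sites record what meets the AE definition, so this is a drafting gap rather than a demonstrated effect.

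**Conclusion.** The conflict is real and, in the supplied text, unreconciled. It concerns declines that are unequivocally due to disease or progression and fall outside the exceptions in 8.3.9. For those, the AE record depends on which section a site applies.

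Each such patient shifts a preferred-term rate by 3.8 to 10 points, depending on the cohort, with planned evaluable numbers as denominators. The total effect cannot be estimated from the documents. The percentage of patients with any AE probably changes little, since a patient may well have another AE, and DLTs should not change. The conclusion rests on the supplied text and would need revisiting if Appendix B settles precedence. This is a wording defect worth correcting because it touches a safety endpoint in small cohorts and costs almost nothing to remove; it does not undermine the safety analysis as a whole.

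**What to change.** Reconcile the passages by replacing the last sentence of Protocol 8.2.7 with: *A clinically significant worsening of performance status from baseline (last pre-dose value) is reported as an AE unless unequivocally due to the disease under study or its progression, subject to the exceptions in 8.3.9 (see 8.3.7, 8.3.9 and 8.3.10).* State in the same place what counts as significant; without that, variation between sites remains.

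All scores stay in the CRF and are still reported under SAP 4.2.3.8, so no performance-status data are lost, and drug-related declines remain AEs. The cost is one amended sentence, a definition, and matching CRF completion guidance. Appendix B should be checked at the same time so that its AE definition agrees.

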8.2.8 Other safety assessments

8.2.8.1 Other assessments

If new or worsening pulmonary symptoms (eg, dyspnea) or radiological abnormality suggestive of pneumonitis/ILD is observed, toxicity management as described in detail in the TMGs (see Section 8.4.5) will be applied. The results of the full diagnostic workup (including high-resolution computed tomography [HRCT], blood and sputum culture, hematological parameters, etc) will be captured in the CRF. It is strongly recommended to perform a full diagnostic workup, to exclude alternative causes such as lymphangitic carcinomatosis, infection, allergy, cardiogenic edema, or pulmonary hemorrhage. In the presence of confirmatory HRCT scans where other causes of respiratory symptoms have been excluded, a diagnosis of pneumonitis (ILD) should be considered and the TMGs should be followed.

Pneumonitis (ILD) investigation

The following assessments, and additional assessments if required, will be performed to enhance the investigation and diagnosis of potential cases of pneumonitis. The results of the assessment will be collected.

- Physical examination
 - Signs and symptoms (cough, shortness of breath, and pyrexia, etc) including auscultation for lung field will be assessed.
- Saturation of peripheral oxygen (resting and exertion)
- High-resolution CT
- Other items
 - When pneumonitis (ILD) is suspected during study treatment, the following markers should be measured where possible:

- (i) ILD Markers (KL-6, SP-D) and β -D-glucan
- (ii) Tumor markers: particular tumor markers which are related to PD
- (iii) Additional clinical chemistry: c-reactive protein, lactate dehydrogenase.

8.3 Collection of adverse events

The Principal Investigator (PI) is responsible for ensuring that all staff involved in the study are familiar with the content of this section.

The definitions of an AE or SAE can be found in [Appendix B](#).

Adverse events will be reported by the patient or parent(s)/legally authorized representative(s).

The Investigator and any designees are responsible for detecting, documenting, and recording events that meet the definition of an AE or SAE. For information on how to follow-up AEs see Section [8.3.3](#).

8.3.1 Method of detecting AEs and SAEs

Care will be taken not to introduce bias when detecting AEs and/or SAEs. Open-ended and non-leading verbal questioning of the patient is the preferred method to inquire about AE occurrences.

8.3.2 Time period and frequency for collecting AE and SAE information

Adverse events and SAEs will be collected from the time of the patient signing the ICF until the follow-up period is completed 90 days after the last dose of durvalumab or durvalumab + tremelimumab. If an event that starts post the defined safety follow-up period noted above is considered to be due to a late onset toxicity to IP then it should be reported as an AE or SAE as applicable.

All SAEs will be recorded and reported to the Sponsor or designee within 24 hours, as indicated in [Appendix B](#). The Investigator will submit any updated SAE data to the Sponsor or designee within 24 hours of it being available.

Investigators are not obligated to actively seek AE or SAE in former study patients. However, if the Investigator learns of any SAE, including a death, at any time after a patient's last visit and he/she considers the event to be reasonably related to the Study treatment or study participation, the Investigator should notify the Sponsor or designee.

The method of recording, evaluating, and assessing causality of AE and SAE and the procedures for completing and transmitting SAE reports are provided in [Appendix B](#).

8.3.3 Follow-up of AEs and SAEs

After the initial AE/SAE report, the Investigator is required to proactively follow each patient at subsequent visits/contacts. All SAE/non-serious AEs/AEs of special interest (AESI; as defined

in Section 8.3.13), will be followed until resolution, stabilization, the event is otherwise explained, or the patient is lost to follow-up.

Any AEs that are unresolved at the patient's last visit in the study are followed up by the Investigator for as long as medically indicated (this may be beyond the 90 days after the last dose of durvalumab or durvalumab + tremelimumab), but without further recording in the CRF. AstraZeneca retains the right to request additional information for any patient with ongoing AE(s)/SAE(s) at the end of the study, if judged necessary.

8.3.4 Adverse event data collection

The following variables will be collected for each AE:

- Adverse event (verbatim)
- The date when the AE started and stopped
- The maximum NCI CTCAE grade reported
- Changes in NCI CTCAE grade (report only the maximum NCI CTCAE grade for a calendar day)
- Whether the AE is serious or not
- Investigator causality rating against the IPs (yes or no)
- Action taken with regard to IPs
- Administration of treatment for the AE
- Outcome.

In addition, the following variables will be collected for SAEs:

- Date the AE met criteria for SAE
- Date the Investigator became aware of the SAE
- Seriousness criteria
- Date of hospitalization
- Date of discharge
- Probable cause of death
- Date of death

- Whether an autopsy was performed
- Causality assessment in relation to study procedure(s)
- Causality assessment in relation to other medication, as explained in Section 8.3.5
- Description of the SAE.

The grading scales found in the revised NCI CTCAE version 5.0 will be utilized for all events with an assigned CTCAE grading. For those events without assigned CTCAE grades, the recommendation in the CTCAE criteria that converts mild, moderate, and severe events into CTCAE grades should be used. A copy of the NCI CTCAE version 5.0 can be downloaded from the Cancer Therapy Evaluation Program website (<http://ctep.cancer.gov>).

8.3.5 Causality collection

The Investigator will assess causal relationship between IP and each AE, and answer ‘yes’ or ‘no’ to the question ‘Do you consider that there is a reasonable possibility that the event may have been caused by the investigational product?’

For SAEs, causal relationship will also be assessed for other medication and study procedures. Note that for SAEs that could be associated with any study procedure the causal relationship is implied as ‘yes’.

A guide to the interpretation of the causality question is found in [Appendix B](#) to the Clinical Study Protocol.

8.3.6 Adverse events based on signs and symptoms

All AEs spontaneously reported by the patient or parent(s)/legally authorized representative(s), or reported in response to the open question from the study site staff: ‘*Have you/the child had any health problems since the previous visit/you were last asked?*’, or revealed by observation will be collected and recorded in the CRF. When collecting AEs, the recording of diagnoses is preferred (when possible) to recording a list of signs and symptoms. However, if a diagnosis is known and there are other signs or symptoms that are not generally part of the diagnosis, the diagnosis and each sign or symptom will be recorded separately.

8.3.7 Adverse events based on examinations and tests

The results from the Clinical Study Protocol mandated laboratory tests and vital signs will be summarized in the clinical study report (CSR). Deterioration as compared to baseline in protocol mandated laboratory values, vital signs, physical examination findings, or ECG should therefore only be reported as AEs if they fulfill any of the SAE criteria or are the reason for discontinuation of treatment with the IP.

If deterioration in a laboratory value/vital sign is associated with clinical signs and symptoms, the sign or symptom will be reported as an AE and the associated laboratory result/vital sign will be considered as additional information. Wherever possible, the reporting Investigator uses the clinical, rather than the laboratory term (eg, anemia versus low hemoglobin value). In the

absence of clinical signs or symptoms, clinically relevant deteriorations in non-mandated parameters should be reported as AE(s).

Deterioration of a laboratory value, which is unequivocally due to PD, should not be reported as an AE/SAE.

Any new or aggravated clinically relevant abnormal medical finding at a physical examination as compared with the baseline assessment will be reported as an AE unless unequivocally related to the disease under study, see Sections 8.3.9 and 8.3.10.

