8.2.1 Physical examinations

Full and targeted physical examinations will be performed according to the assessment schedules (see the SoAs) and in unscheduled visits. Full physical examinations will include assessments of the head, eyes, ears, nose, and throat and the respiratory, cardiovascular, GI, urogenital, musculoskeletal, neurological, dermatological, hematologic/lymphatic, and endocrine systems. Height and weight will be measured at screening, and q4w (on dosing days only). Targeted physical examinations are to be utilized by the Investigator on the basis of clinical observations and symptomatology. Situations in which physical examination results should be reported as AEs are described in Section 8.3.7.

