4.2.3.5 Physical examination

Physical examination findings will be reported as adverse events.

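### Protocol 8.3.7 gives opposite AE-reporting rules for non-serious, clinically relevant physical-examination findings, and the SAP's handling of examinations works under only one of them

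*Protocol*

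**What the plan says.** Protocol Section 8.2.1 sends sites to one place for the rule: "Situations in which physical examination results should be reported as AEs are described in Section 8.3.7".

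Section 8.3.7 then gives two rules. Its first paragraph states that laboratory tests and vital signs will be summarised in the CSR. It then limits AE reporting of deteriorations from baseline in four kinds of data, the last two being covered by these words: "physical examination findings, or ECG should therefore only be reported as AEs if they fulfill any of the SAE criteria". The one other case it admits is a finding that causes IP to be stopped. Its last paragraph says: "Any new or aggravated clinically relevant abnormal medical finding at a physical examination as compared with the baseline assessment will be reported as an AE", with a single exception, "unless unequivocally related to the disease under study".

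Physical examination is a named safety endpoint, listed next to AEs and not as part of them. For dose-finding, Protocol Section 3 states: "Endpoints include AEs, vital signs, physical examinations, ECGs, and laboratory evaluations". The same five items are the endpoint for the dose-expansion safety objective, and the SAP repeats them in its Section 1.1.

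SAP Section 4.2.3.5 consists of one sentence: "Physical examination findings will be reported as adverse events". The SAP amendment history (entry of 08JUN2021) gives the reason: the listing of examination data was taken out because any finding is an AE.

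**The concern.** The site is sent to a section that tells it both to report and not to report the same finding. The restriction in the first paragraph is argued from data that have their own CSR summaries. That argument works for laboratory values and vital signs, but physical examination is not part of it, and under the SAP it has no summary of its own.

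What is at stake is the consistency of the safety data. Targeted examinations are scheduled at every treatment visit in both phases (Protocol Tables 1 and 2), so the choice between the two rules recurs throughout the study. Sites that read the section differently would produce different AE counts from the same clinical picture, and the tables would not show it. The study is the first to give this combination to children, the cohorts are small and safety is a primary objective of dose-finding, so the AE data should rest on one rule.

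**Working it through.** No arithmetic applies and the plan gives no figure to reproduce. The check sets the two rules side by side and then follows a finding to the outputs.

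**Step 1: where the rules agree and where they do not.**

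| Examination finding, new or worse than baseline | 8.3.7, first paragraph | 8.3.7, last paragraph |
|---|---|---|
| Clinically relevant, serious, not due to the disease | Report | Report |
| Clinically relevant, non-serious, reason for stopping IP, not due to the disease | Report | Report |
| Clinically relevant, non-serious, IP continues, not unequivocally due to the disease | Do not report | Report |
| Clinically relevant, non-serious, IP continues, unequivocally due to the disease | Do not report | Exempt |
| Not clinically relevant, non-serious, IP continues | Do not report | Silent |

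Only the third row is a contradiction. It cannot be removed by arguing that a new finding is not a deterioration from baseline. The last paragraph also covers aggravated findings, and an aggravated finding is a deterioration on any reading.

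**Step 2: does the stated rationale reach examinations?** The premise names laboratory tests and vital signs. The conclusion adds physical examination and ECG. SAP Sections 4.2.3.3, 4.2.3.4 and 4.2.3.6 specify listings and summaries for laboratory data, vital signs and ECG. Section 4.2.3.5 specifies none for examinations. Of the four items in the restriction, examination is the only one with no specified output apart from AEs.

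**Step 3: where a third-row finding ends up.** Under the last paragraph it enters the AE data and so the AE tables. If its term belongs to an AESI category it also enters the AESI tables and the sponsor's imAE review (SAP Section 3.3.1). Under the first paragraph it is not an AE, and no examination table or listing is specified for it. The SAP's reason for dropping the listing is true only if the last paragraph governs.

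**Step 4: do the protocol and SAP otherwise agree?** Protocol Section 9.4.2.2 includes physical examinations among the change-from-baseline summaries, and Section 9.5.2 counts them as safety data apart from AEs. SAP Section 6, which lists changes from the protocol, does not mention that this output was dropped.

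**The case against.** The strongest reply is that the intended rule is clear. The last paragraph deals with physical examination alone, while the first is a general clause covering four kinds of data, so the specific rule should prevail. The SAP amendment history shows that the sponsor reads it that way. This stands as evidence of intent. It does not settle what a site does, because the first paragraph names physical examination expressly and nothing in the section gives the last paragraph priority.

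A second reply is that other routes exist. Protocol Section 8.3.6 has AEs that come to light through observation recorded in the CRF, which fits a rash seen by staff but not mentioned by the family. Section 8.3.13 says an AESI may be non-serious and describes rapid reporting of AESIs. TSH is measured every 4 weeks, so detection of thyroid dysfunction does not depend on palpation. All of this stands, and it limits the consequence. It also means that Section 8.3.6 sits uneasily with the first paragraph of 8.3.7, which is a further reason to reconcile them.

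A reader might infer that the affected findings vanish from the database or are recorded nowhere. The documents do not support that. Protocol Section 9.4.2.1 and SAP Section 3.3 say physical examinations are collected for all patients, and Protocol Section 9.5 and SAP Section 4.1 promise a listing of all data. A reader might also infer a broad fall in AESI and imAE counts. Among findings likely to be seen only on examination, rash is the clear case of a named AESI category, so the general claim is not shown.

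**Conclusion.** The contradiction is real and confined to one class: clinically relevant examination findings that are non-serious, do not lead to stopping IP and are not unequivocally due to the disease. For these, Section 8.3.7 gives incompatible instructions, and the SAP's treatment of a named safety endpoint is sound under only one of them. Findings handled under the first paragraph can be missing from the AE tables (and from the AESI and imAE tables where relevant, such as rash) and have no dedicated examination output.

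The size of the loss cannot be estimated. The documents give no frequency for such findings, no share detected only on examination and no indication of which paragraph sites follow, and Section 8.3.6 may recover some. Any patient count would rest on assumed rates alone.

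The conclusion rests on the wording of Section 8.3.7 and SAP Section 4.2.3.5. The AE definition in Appendix B and the CRF were not available for this check; either could narrow the practical effect, but neither would remove the conflict within 8.3.7. The point should be corrected. It does not touch the efficacy analysis.

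**What to change.** Delete physical examination findings from the restriction in the first paragraph of Protocol Section 8.3.7, so that the last paragraph and SAP Section 4.2.3.5 govern. This is a three-word deletion, makes the SAP's premise true, and costs somewhat more AE entry at sites.

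If the restriction is to stay, reinstate a physical-examination listing in the SAP. That is one extra output, but it is the weaker remedy: it shows the findings without bringing them into the AE, AESI or imAE tables.

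In either case, bring Protocol Sections 9.4.2.2 and 9.5.2 into line with the SAP, or record the dropped examination summary in SAP Section 6. For data already collected, a check for recorded examination findings that have no matching AE would show whether any were missed.
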